5.3 Screen Failures

Participants who provide informed consent, but who are not ultimately randomized in the Active Study (Section [4.10](#)), will be considered screen failures and will remain in the screening segment of the data system. The reason for screen failure will be captured in the data system.

5.4 Treatment Assignment Procedures

5.4.1 Randomization Procedures

Eligible participants will be randomly assigned in a 2:1 ratio to either GIR or placebo. The participant's randomized treatment assignment will be obtained through the Advantage eClinical® enrollment module. In the event that Advantage eClinical® is not available at the time of randomization, a back-up system specified in the MOP will be used. Randomization will be stratified by study site. The randomization procedure will be conducted centrally through the study data system and randomization assignments will not be conveyed to participants or study sites. The DCC statistician will generate the randomization schedule using balanced blocks within site to ensure relative equality of assignment across treatment groups. A DCC statistician will review randomization data on a regular basis to ensure that the scheme is being implemented according to plan. A randomization assignment, once issued, will not be re-allocated. Details of the randomization process are described in a separate Randomization Plan.

5.5 Participant Discontinuation/Withdrawal

5.5.1 Participant/Parent/Legal Guardian Decides to Withdraw Consent

Participants or their parent/legal guardian may voluntarily withdraw consent to participate in the study at any time. Participants or their parent/legal guardian are not obligated to state the reason for withdrawal. The reasons for withdrawal, or failure to provide a reason, must be documented by the investigator. No additional study procedures or data should be collected after consent has been withdrawn.

5.5.2 Participant/Parent/Legal Guardian Decides to Withdraw from Study Product

Participants or their parent/legal guardian may also withdraw from receiving the study product for any reason but continue to be followed for safety, including safety ESIs.

Participants or their parent/legal guardian are not obligated to state the reason for withdrawal.

At the time of withdrawal from study product, participants (and site staff) will be unmasked and asked to complete an electrocardiogram (ECG), as well as provide a PK blood sample. Participants, who were randomized to receive GIR, will be transitioned off of GIR according to the dose taper process described in Section [6.13.2](#) followed by a final telephone safety assessment 5 (+ 2) days after the final study dose administered. Participants who were randomized to receive placebo will have a final telephone safety assessment 5 (+ 2) days after final study dose administered. The parent/legal guardian will be asked to complete the Aberrant Behavior Checklist (ABC) and the treating clinician will be asked to perform a CGI-I. Unmasking should only occur following completion of the other Early Withdrawal / Termination Visit Assessments (Section [6.6](#)). Refer to the MOP for details.

5.5.3 Study Investigator/Sponsor Decides to Withdraw Participant

The study doctors or sponsor may decide to take the participant out of this study without consent if:

- Participant's condition changes and the study is no longer in their best interest
- Participant/parent/legal guardian non-compliance with the study protocol
- The entire study is stopped by the FDA or the sponsor

A participant may be withdrawn from receiving study product if they experience a clinically significant AE that requires discontinuation of treatment, at the discretion of the study doctor or sponsor.

If any of the above occurs, the participant/parent/legal guardian will be informed and the investigator will discuss other options.

5.6 Handling of Withdrawals

The reasons for withdrawal, or failure to provide a reason, must be documented by the investigator.

Reasons of withdrawal may include:

- Parents/legal guardians of participants who withdraw consent and request no further follow-up
- If minor participants decide not to remain in the study, they will be withdrawn even if the parent/legal guardian of the minor participant has not withdrawn consent.
- Study Investigator/Sponsor decision

5.6.1 Early Withdrawal/Discontinuation Assessments

Refer to Section [6.13.2](#) for study product taper requirements. The following assessments will be collected at the time of early termination/withdrawal: ABC, ECG, a PK blood sample, and CGI-I. If a participant/legal guardian withdraws consent, no further follow-up will occur following withdrawal of consent. Participants who are discontinued from study drug due to an AE, whether serious or non-serious, must be followed by the investigator until the AE is resolved or considered stable. The medical monitor (MM) or study investigator must be notified if the AE may relate to overdose of study treatment; the package insert should be consulted for details of any specific actions to be taken.

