3 OBJECTIVES AND OUTCOME MEASURES

	Objectives	Outcome Measure(s)	Endpoint(s)
Primary Objective:	Determine efficacy of GIR for the treatment of hyperactivity/impulsivity and inattention in children with DS after 8 weeks of treatment.	Primary Efficacy Outcome Measure: Parent-rated ABC-H subscale score Secondary Efficacy Outcome Measure: CGI-I specific to hyperactivity, inattention and impulsivity behaviors	Primary Endpoint: Change from baseline to Week 8 of the ABC-H subscale score Secondary Efficacy Endpoints: Change from baseline to Week 4 of the ABC-H subscale score. Proportion of participants with a CGI-I score of 2 or better at Week 4 and Week 8.
Secondary Objective:	Characterize the safety profile of GIR in children with DS.	
 • Adverse Events (AEs) • Serious Adverse Events (SAEs) • Safety Events of Special Interest (ESIs) 	Incidence of AEs, SAEs, and safety ESIs through Week 8
Exploratory Objective 1:	Characterize GIR exposure in children with DS.	Guanfacine HCl plasma concentration	Guanfacine HCl exposure at Week 4 and Week 8 as indicated by the following endpoints: 
 • Steady state peak drug concentration ($C_{max,ss}$) • Time at peak concentration ($T_{max,ss}$) • Minimum concentration ($C_{min,ss}$) • Apparent area under the concentration versus time curve at steady state (AUC_{ss}/F) • Apparent clearance (CL_{ss}/F) • Volume of distribution (V/F) • Half-life ($t_{1/2}$)
Exploratory Objective 2:	Characterize the exposure-response relationship of GIR for the treatment of hyperactivity/impulsivity, inattention, and sleep quality in children with DS.	
 • Guanfacine HCl plasma concentrations ($C_{max,ss}$ and $C_{min,ss}$) • Area under the concentration time curve (AUC_{ss}) • ABC-H subscale score • CGI-I • Epworth Sleepiness Scale for Children and Adolescents (ESS-CHAD) • Child's Sleep Habits Questionnaire (CSHQ) 	Change in behavioral and sleep scales (ABC-H, CGI-I, ESS-CHAD, and CSHQ) relative to Guanfacine HCl plasma concentration ($C_{max,ss}$ and $C_{min,ss}$) and AUC_{ss} at Week 4 and Week 8

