6.6 Early Withdrawal / Termination Visit

If a participant withdraws from study product administration or terminates from the study early, the study team will attempt to collect the following at an in-person visit, if an in-person visit is not feasible, a telephone assessment will occur to obtain the following assessments/procedures:

- Safety Events, including AEs, SAEs, and safety ESIs
- ECG (in-person only)
- Parent/legal guardian-completed ABC (Section [0](#))
- Clinician-completed CGI-I (Section [6.9.3](#))
- Blood collection for PK analysis (in-person only)
- Unmasking of participant and manage GIR Taper/Bridge per Section [6.4](#). Unmasking should only occur following completion of the other Early Withdrawal / Termination Visit Assessments above.

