6.9 Clinical Outcome Assessments

Identifying measures to evaluate cognition and behavior in children with IDD and DS specifically, within clinical trials has traditionally been challenging.¹⁰ Leading clinician and scientist experts were assembled by the NIH to review existing measures and identify those that are appropriate for clinical trials in individuals with IDD and specifically DS.¹¹ The ABC, ESS-CHAD, and CSHQ will be collected using Electronic Participant Reported Outcomes (ePRO), see Section 15.3. Details regarding which individual(s) complete(s) each measure at the various visits are included in [Table 2](#).

Table 2. Frequency of measures and who completes each measure.

Measure	Frequency Parent/ Legal Guardian Completes	Frequency Clinician Completes
ABC (Section 0)	Screening, Week 4, Week 8, Early Withdrawal	N/A
Sleep Assessments (Section 6.9.2)	Day 1, Week 4, Week 8	N/A
CGI-I (Section 6.9.3)	N/A	Weeks 1-8, Early Withdrawal
CGI-S (Section 6.9.3)	N/A	Screening

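### ESS-CHAD and CSHQ are not scheduled at early withdrawal, so children who stop before Week 4 have no post-baseline sleep score and later stoppers have none at the time of stopping

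*Combined protocol and SAP*

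**What the plan says.** Section 5.6.1 lists what is taken when a child leaves early: "The following assessments will be collected at the time of early termination/withdrawal: ABC, ECG, a PK blood sample, and CGI-I". Section 6.6 gives the same list plus safety events and unmasking, and allows a remote route: "if an in-person visit is not feasible, a telephone assessment will occur to obtain the following assessments/procedures". At that visit the ECG and PK sample are in person only, and unmasking comes last.

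In Table 2 the sleep assessments are due on "Day 1, Week 4, Week 8", while the ABC is due at "Screening, Week 4, Week 8, Early Withdrawal". CGI-I also carries an early withdrawal entry. The sleep row of Table 1 has no mark in the early withdrawal column.

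Under section 5.5.2 participants "may also withdraw from receiving the study product for any reason but continue to be followed for safety, including safety ESIs". No later sleep assessment is stated for them.

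The sleep scales serve Exploratory Objective 2 (section 3): "Characterize the exposure-response relationship of GIR for the treatment of hyperactivity/impulsivity, inattention, and sleep quality in children with DS". Its endpoint is "Change in behavioral and sleep scales (ABC-H, CGI-I, ESS-CHAD, and CSHQ) relative to Guanfacine HCl plasma concentration" and AUC at Weeks 4 and 8. Section 10.4.3 analyses both scales with a mixed model like that for the primary outcome, and ESS-CHAD also as a binary outcome with a cut at 10.

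**The concern.** At withdrawal the plan takes the exposure measurement and both behavioural responses but neither sleep response. Sleep is thus the one part of Exploratory Objective 2 with nothing to set against the withdrawal PK sample.

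The loss may also be informative. Sedation is a listed reaction to the drug (section 2.4.2), section 6.13.1 has a specific step for it, and section 5.5.3 allows treatment to be stopped for a clinically significant adverse event. If a child stops because of sleepiness, the missing value is the one ESS-CHAD was meant to record. At stake are the ESS-CHAD comparison between arms, the proportion scoring 10 or more, and the relation of exposure to sleepiness. The scores cannot be collected afterwards.

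**Working it through.** **1. Schedule side by side** (Tables 1 and 2, sections 5.6.1 and 6.6)

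| Measure | Before first dose | Week 4 | Week 8 | Early withdrawal |
|---|---|---|---|---|
| ABC | Screening | yes | yes | yes |
| CGI-I | not applicable | yes | yes | yes |
| PK sample | no | yes | yes | yes, in person |
| ESS-CHAD, CSHQ | Day 1 | yes | yes | **no** |

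**2. The plan's own figures** (sections 4.2.1 and 10.6). The assumed effect is d = (26 − 20.6)/6 = 0.90. With 48 evaluable children split 32:16 and two-sided alpha 0.05, the noncentrality is 0.90 × √(32 × 16/48) = 2.94 on 46 degrees of freedom. Power is 82.1%, which agrees with the stated figure of above 80%. Inflation gives 48/(1 − 0.20) = 60. Planned dropout is 0.20 × 60 = 12 children. At 2:1 (40:20) and equal rates this is 8 on GIR and 4 on placebo. All 12 would lack a Week 8 sleep score.

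**3. How many have no post-baseline sleep score.** The documents do not give the share s of dropouts who stop before Week 4, so s is varied. The counts are 12 × s overall and 8 × s on GIR.

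| s (assumed) | No post-baseline sleep score | of these on GIR | Week 4 score only |
|---|---|---|---|
| 0% | 0 | 0 | 12 |
| 25% | 3 | 2 | 9 |
| 50% | 6 | 4 | 6 |
| 75% | 9 | 6 | 3 |
| 100% | 12 | 8 | 0 |

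The window is not trivial. Escalation is assessed every 5 (+2) days from Day 1. If every step is taken, 5-day steps fall on Days 6, 11, 16 and 21 (dose level 5 of 6), and 7-day steps on Days 8 and 15 (level 3). Much of the escalation can precede the first post-dose sleep score.

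**4. Possible effect on the GIR proportion with ESS-CHAD of 10 or more.** Let f be the share of the arm with no post-baseline score, p the proportion sleepy among children with a score, and q the proportion among those without. The full-arm value is (1 − f)p + fq, the observed value is p, and the understatement is f(q − p). All p and q are assumptions; f = 8/40 = 0.20 is the upper bound from step 3 under equal dropout.

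- f = 0.20, p = 20%, q = 50% to 100%: full-arm value 26% to 36% against 20% observed, an understatement of 6 to 16 points.
- f = 0.20, p = 10%: 8 to 18 points. With p = 30%: 4 to 14 points.
- f = 4/40 = 0.10, p = 20%: 3 to 8 points.
- f = 0, or q = p: none.

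The error in the between-arm difference is this amount less the corresponding amount in placebo, for which the documents give no basis.

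**5. What the mixed model can do.** A child with only a Day 1 score supplies no post-dose outcome. The model then takes the missing scores to be like those of children in the same arm with the same baseline. That fails if stopping depended on sleepiness after dosing. For a child who stops after Week 4, the Week 4 score enters the model and carries part of that information.

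**The case against.** The four places agree, so this is a consistent design choice. The protocol deliberately limits assessment burden: under section 15.7 most missing outcome assessments are not deviations, to help retention. The analyses affected are exploratory, and section 10.4.3 says only that the exposure-response analysis may be done. All of this stands, and it sets the priority.

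Several stronger readings are tempting, and the documents do not support them.

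- A reader might infer that children who stop for sedation vanish from the sleep and exposure-response results altogether. They do not. Those who stop after Week 4 keep their Week 4 sleep and PK data. ABC, CGI-I and (in person) PK are taken at withdrawal, and one evaluable sample suffices for the PK population (section 10.3.3). How off-schedule values enter endpoints defined at Weeks 4 and 8 is, however, not stated.
- A reader might infer that the sedation signal is hidden. Sedation, drowsiness and sleep trouble are solicited Yes/No at the weekly assessments, rated for intensity and causality (section 7.1.2), and collected at the withdrawal visit (section 6.6). Section 10.4.2 plans models for them. This does not supply a scale total, a change from Day 1 or a classification at 10, so it does not replace ESS-CHAD.
- A reader might infer that loss is heavier on GIR and flatters every sleep result. The documents give no rate of stopping for sedation and no arm difference. The 20% is all-cause, section 2.4.2 calls most reactions mild and passing, and section 6.13.1 offers steps short of stopping. The direction is plausible for ESS-CHAD, which measures daytime sleepiness. It is not established for CSHQ, which covers bedtime, sleep behaviour, night waking and morning waking.

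Replacement of withdrawn children (section 5.6.2) restores numbers but not the missing scores.

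**Conclusion.** The gap is real but narrow, and it is confined to exploratory analyses. The 12 children without a Week 8 sleep score follow from the plan's own dropout figure; the 8 on GIR also assume equal dropout by arm. The 0 to 12 with no post-baseline score is a range, because the timing of dropout is unknown. An understatement of ESS-CHAD sleepiness, and of its relation to exposure, arises only if some children stop because of sleepiness. Its size in step 4 rests on assumed rates, with the largest values at the upper bound where every GIR dropout precedes Week 4. It is a possibility to guard against, not a demonstrated bias. Primary and secondary endpoints and the sample size are untouched.

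**What to change.** Add parent-completed ESS-CHAD and CSHQ to the early withdrawal assessments in Table 1, Table 2, 5.6.1 and 6.6, and align the list in 5.5.2. Have them completed before unmasking, like the ABC, in person or by ePRO or telephone, unless consent has been withdrawn.

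State in the analysis plan, before data lock, how these scores enter the sleep mixed models: at the actual assessment time or at the nearest scheduled visit. Pair them with the withdrawal PK sample where one was drawn in person, and record the time since the last dose, since a score taken well after stopping may not reflect sleepiness on treatment.

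The number of dropouts with no post-baseline sleep score could then fall towards 0. It would not reach 0 where consent is withdrawn or the withdrawal assessment is missed, and telephone visits would yield a sleep score without a PK value. The cost is 8 + 35 = 43 items (section 6.9.2), already on ePRO with paper and telephone options (section 15.3), at a contact where the parent already completes the ABC. The downside is a few extra minutes for a family that is leaving treatment. No sample-size or power figure changes.

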6 STUDY PROCEDURES

6.1 Summary of Procedures

Table 1. Schedule of Study Procedures and Assessments

	Screening	Study Intervention (Weeks 1-3)	Study Intervention (Week 4)	Study Intervention (Weeks 5-7)	Study Intervention (Week 8)	Taper/Bridge	Follow-Up	Early Withdrawal/ Discontinuation
	Day -29 to 0 ¹	Day 1 ¹⁻²¹ (± 1 day)	Day 22-28 (± 3 days)	Day 29-49 (± 1 day)	Day 50-56 (± 3 days)		5 (+ 2) days post final study dose	
Informed consent/assent	X							
Distribution of device for remote HR and BP assessment		X ³						
Demographics	X							
Medical History	X							
Physical Exam	X	X ³						
Weight/height			X		X			
Vital Signs	X	X ³	X		X			
Concomitant Medications of Interest	X		X		X			
ECG	X		X		X			X
Lab assessments	X		X ¹¹					
Pregnancy test ¹³	X							
Blood Collection for PK			X ²		X ²			X ²
Randomization		X ³						
Dose escalation with HR and BP assessment		X ⁴	X ⁴	X ⁴				
Study product administration		X ⁵	X	X	X			
Unmasking					X			X
Study drug taper/bridge						X ⁶		X
Study Diary			Continuous			X ⁶	X ⁶	
CGI-S	X							
CGI-I		X ⁷	X	X ⁷	X			X
ABC	X		X		X			X
asQ Tool ¹²	X		X		X			
Sleep assessments		X ³	X		X			
Safety Events ⁸	X ⁹	X	X	X	X	X	X ¹⁰	X

1 – Day 0 and Day 1 may be the same calendar day.

2 – Preferred sampling: within 60 minutes prior to study product dose or 30-120 minutes after study product dose.

3 – Randomization; distribution of device for remote HR and BP assessment; physical exam, including weight/height; vital signs; and sleep assessments occur only on Day 1 prior to study product administration.

4 – Just prior to dose escalation time point, every 5 (+ 2) days, parent/legal guardian will be asked to measure HR and BP.

5 – Initial dose occurs on Day 1, Day 0 and Day 1 may be the same calendar day. The initial dose will be administered before bedtime on Day 1. Subsequent doses occur according to Section [6.13.1](#).

6 – For GIR arm only. Participants who choose to discontinue GIR will be tapered off study drug at 1 mg every 3 days. Participants who choose to transition to standard of care GIR will continue on up to 7 days of study drug to bridge to standard of care GIR. See Section [6.13.2](#).

7 – Weekly CGI-I, beginning at first weekly telephone assessment.

8 – Includes AEs, SAEs, and safety ESIs, as described in Section [7.1.2](#).

9 – Only AEs directly related to study procedures (e.g., blood collection) during the screening period will be collected.

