6.8 Dose Escalation Assessments

Every 5 (+ 2) days through Week 7, just prior to each dose escalation assessment, parent/legal guardian will be asked to measure HR and BP using the device given to them from the study team at the time of randomization. A telephone or in-person assessment by the treating clinician will occur to determine dose escalation. If the participant reaches the maximum dose of 3 mg/day, prior to Week 7, no dose escalation will occur. Alternatively, a CGI-I will be determined by the treating clinician and any score of 3 or worse (higher) will warrant dose escalation, provided no significant safety concerns exist. AEs and safety ESIs will be recorded to assess safety.

Clinically significant findings that would prevent dose escalation include, but are not limited to:

- CGI-I score of 2 or 1
- HR and BP values that are considered unsafe to dose escalate:
 - Clinically significant hypotension, defined as systolic BP percentile less than the 5th percentile.^{31,34} This corresponds to systolic BP percentiles for neurotypical children under the 8th percentile for males and under the 10th percentile for females.
 - Clinically significant bradycardia, defined as HR > 2 SD below mean for age
- Any AEs or safety ESIs that make it unsafe to dose escalate, at the discretion of the treating clinician
- Any other finding that indicates it is not safe to dose escalate, at the discretion of the treating physician and/or principal investigator (PI).

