7.1.2 Safety Events of Special Interest (ESIs)

A safety ESI is a select safety event that could be related to the study drug. Safety ESIs will be solicited for their occurrence (No or Yes) at weekly dose-escalation assessments, including in-person assessments (Week 4 and Week 8), and the final telephone safety assessment (5 + 2 days) after the final dose of study drug. The safety ESIs documented will be assessed by the investigator/delegate (defined as a clinician licensed to make a diagnosis) for intensity, causality, and association to provide uniform data collection of all events. Any reported ESIs should be managed, as needed, according to clinical judgement and local guidelines.

Safety ESIs include:

- Syncope/passing out
- Sedation
- Trouble falling asleep
- Trouble staying asleep
- Trouble waking up
- Drowsiness
- Decreased Energy/Fatigue
- Trouble concentrating
- Trouble breathing
- Constipation
- Diarrhea
- Nausea
- Vomiting
- Skin rash
- Itching
- Change in appetite
- Anxious/fearful

- Sadness/depressed mood
- Self-injurious behavior
- Clinically significant hypotension, defined as systolic BP percentile less than the 5th percentile.^{31,34} This corresponds to systolic BP percentiles for neurotypical children under the 8th percentile for males and under the 10th percentile for females.
- Clinically significant bradycardia, defined as HR > 2 SD below mean for age

The following safety ESIs will only be assessed at in-person visits (Week 4 and Week 8):

- Any clinically significant cardiac event (e.g., clinically significant changes on ECG)
- Suicidality via the asQ Tool (see Section [6.10](#))

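### No blood pressure is scheduled at early withdrawal, so a child who stops within 5–7 days of a dose step, away from the Week 4 visit, has no scheduled reading at that dose

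*Combined protocol and SAP*

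**What the plan says.** **Exit assessments.** Three sections of the protocol list what is done when a child stops early, and none includes BP or vital signs.
- Section 5.6.1: "The following assessments will be collected at the time of early termination/withdrawal: ABC, ECG, a PK blood sample, and CGI-I".
- Section 5.5.2, on stopping study product: the child is "asked to complete an electrocardiogram (ECG), as well as provide a PK blood sample". The ABC and CGI-I are added later in the same section.
- Section 6.6: safety events including ESIs, ECG, ABC, CGI-I, PK sample, then unmasking. The visit may be remote: "if an in-person visit is not feasible, a telephone assessment will occur to obtain the following assessments/procedures". The ECG and PK sample are then not obtained.

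In Table 1, the Vital Signs row and the row for dose escalation with HR and BP are both blank under Early Withdrawal/Discontinuation. The Safety Events row is marked there.

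**The ESI.** Section 7.1.2 lists "Clinically significant hypotension, defined as systolic BP percentile less than the 5th percentile".

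**When BP is scheduled.** Clinic vital signs are at Screening, Day 1, Week 4 and Week 8. Home readings are tied to the escalation contacts. Table 1, footnote 4, reads: "Just prior to dose escalation time point, every 5 (+ 2) days, parent/legal guardian will be asked to measure HR and BP". Section 6.8 says the same and ends these contacts at Week 7.

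**The concern.** The exit visit asks for an event whose definition needs a measurement that the visit does not schedule. The Week 8 visit (Section 6.3) pairs ECG, PK, ABC and CGI-I with vital signs; the exit visit keeps those four and omits vital signs.

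The drug makes this relevant. Guanfacine is an antihypertensive, and Section 2.4.2 lists lowered BP as a risk. Section 2.1.1 notes that children with Down syndrome have lower BP profiles than age-matched controls and that this raises concern about hypotension. Section 4.4 justifies the taper by rebound hypertension.

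Home BP is read just before a step, so the first scheduled reading at a new dose comes 5 to 7 days after that dose begins. A child who stops inside that window has a last scheduled reading from one 0.5 mg level lower or, before the first contact, from Day 1. For such a child one component of the secondary safety objective rests on unscheduled readings, whereas a completer has a clinic BP at Week 8.

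**Working it through.** **1. The plan's own figure.** Section 10.6 gives 48 evaluable children and 20% dropout: 48 / (1 − 0.20) = 60, as stated. Its effect size also reproduces: (26 − 20.6) / 6 = 0.90. At 32:16 the two-sample t-test has power 0.821, above the stated 80%. The present point changes none of this; it borrows only the 20%.

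**2. The unread windows.** With uninterrupted escalation through the six levels of Table 3:

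| Step | Level starts (Day) | First scheduled home BP at that level (Day) |
|---|---|---|
| 5 days | 1, 6, 11, 16, 21, 26 | 6, 11, 16, 21, 26, 31 |
| 7 days | 1, 8, 15, 22, 29, 36 | 8, 15, 22, 29, 36, 43 |

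A child who stops at a contact has a reading. A child who stops between the two days for a level has none scheduled, unless the Week 4 visit falls in between.

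**3. Share of treatment time unread.** Unread days = levels × gap; share = unread days / 56.
- Two levels, 5-day gap: 2 × 5 = 10; 10/56 = 17.9%.
- Three levels, 7-day gap: 3 × 7 = 21; 21/56 = 37.5%.
- Six levels: 6 × 5 = 30 to 6 × 7 = 42; 30/56 = 53.6% to 42/56 = 75%.

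Two to three levels (1.0–1.5 mg/day) is an assumption, prompted by the average of 1.1 mg/day in the earlier Down syndrome study cited in Section 10.6. Six levels is the most the plan allows.

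**4. Children affected.** GIR dropouts, taking 20% as equal by arm (assumed): 60 × 0.20 × 2/3 = 8. With stop days spread evenly over 56 days (assumed), affected = dropouts × share.

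| Dropout | GIR dropouts | 2–3 levels | 6 levels |
|---|---|---|---|
| 10% | 4 | 0.7–1.5 | 2.1–3.0 |
| 20% | 8 | 1.4–3.0 | 4.3–6.0 |
| 30% | 12 | 2.1–4.5 | 6.4–9.0 |

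For the 20% row: 8 × 10/56 = 1.43, 8 × 21/56 = 3.00, 8 × 30/56 = 4.29, 8 × 42/56 = 6.00. The 10% and 30% rows are assumed alternatives.

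**5. Subtractions.**
- *Consent withdrawals.* Section 5.5.1: "No additional study procedures or data should be collected after consent has been withdrawn". If these are 25–50% of the 8 (assumed), 6 to 4 remain. Then 4 × 10/56 = 0.7 to 6 × 21/56 = 2.3 at two to three levels, and 4 × 30/56 = 2.1 to 6 × 42/56 = 4.5 at six.
- *Week 4 vital signs.* The visit (Day 22–28, ± 3) can fall from Day 19 to Day 31. One visit can shorten at most one window per child, so it removes at most 7 of 56 days, or 8 × 7/56 = 1.0 child. At two to three levels without holds it matters only for 7-day steps, where the third window is Days 15–22.

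**The case against.** The strongest reply is that the plan already leads a site to a BP value.
- ESIs are collected at exit, and answering the hypotension item properly requires a reading.
- The history of changes (v3.0) says HR and BP were added to the Study Diary. The diary runs through treatment and taper and is reviewed at the final call (Section 6.5).
- Under Section 5.6.1, a child stopped for an adverse event "must be followed by the investigator until the AE is resolved or considered stable".
- Section 6.13.1 has doses held, re-divided or reduced when a safety concern arises, which would often come before a stop.
- Section 5.5.2 refers to the MOP, which was not available and may add vital signs.

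All of this stands as mitigation, but none of it sets a reading at exit. The diary provides a place to record BP, while the request to measure is tied to escalation contacts. Adverse-event follow-up covers only recognised events and names no BP. The hold-or-reduce steps do not bind a parent, who may stop study product for any reason.

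Two further objections also stand. Section 10 defines no endpoint of BP at last dose; the endpoint is ESI incidence. And an exit reading may be off drug: a taper is prescribed only above 1 mg/day, so a child at the first two levels may already have stopped.

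A reader might infer that hypotension will be under-counted on guanfacine. The documents do not support that: a missing reading is not a missed event, they give no hypotension rate, and symptoms such as syncope, sedation and drowsiness are solicited without a cuff. Nor do early stoppers lack BP data altogether; they have the baseline and every reading before the last step.

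**Conclusion.** The gap is real and minor. As written, a child who stops after a dose step and before the next contact, away from the Week 4 visit, has no scheduled BP at the stopped dose, although the exit visit collects an ESI defined by BP.

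The size cannot be fixed from the documents. The range of 1.4–3.0 children at two to three levels is not a ceiling, because the plan permits six levels. That case gives 4.3–6.0 of 8 before the subtractions shown. Both ranges depend on equal dropout by arm, evenly spread stop days and no dose holds, none of which the documents establish. The 20% itself is an allowance for sample size, not a forecast of stops between contacts. The earlier study's low average dose is weak support for two to three levels, because Section 2.2 says it had no scheduled dose increases, whereas here a CGI-I of 3 or worse warrants escalation.

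The primary endpoint, sample size and power are unaffected. Heart rate is less exposed than BP, since an in-person exit has an ECG; a telephone exit loses both.

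**What to change.** Add HR and BP to the lists in Sections 5.5.2, 5.6.1 and 6.6, and mark them in the Early Withdrawal column of Table 1. Take them before unmasking and before any taper begins. For a telephone exit, ask the parent for a home-device reading at that contact. Record the time since the last full dose, so that a reading taken after dosing has stopped is not reported as BP on that dose.

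The burden on families is low: an in-person exit already has an ECG and a blood draw, and the home device is handed out on Day 1. The cost is a minor amendment, with approval by the central IRB and submission to each site's IRB (Section 14.3) at about 17 sites. It is best bundled with the next amendment.
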